Hematopoietic stem cell transplantation (HSCT), either autologous or allogenic, is a treatment strategy widely used in the onco-hematology field and less often for other diseases¹. The most employed source of stem cell is peripheral blood stem cell (PBSC) identified as circulating CD34+ cells and collected by leukapheresis (LP) following mobilization process using granulocyte-colony stimulating factor (G-CSF) alone or in association with chemotherapy and/or plerixafor, the latter in case of poor-mobilizer patients².

The PBSC harvest needs dedicated platform for being properly performed: in our institution the Spectra Optia apheresis system (Terumo BCT) is routinely employed with a continuous mononuclear cells collection (cMNC) system. Spectra Optia (Terumo BCT) is designed to optimize PBSC harvest through automated buffy coat interface identification and management, low volume tubing set, low extracorporeal volumes and support of cMNC processing system³. In the dual-step mononuclear cells collection (MNC) system an intermediate chamber is used to collect white blood cells while returning the majority of platelets to the subject. Then optical sensors detect red blood cells (RBC) overflow and leucocytes are intermittently flushed in the collection bag. The cMNC system differs from the former dual-step system by eliminating the intermediate collection chamber used and thus allowing continuous collection of leucocytes from the buffy coat. This approach appears to be less time consuming, more manageable, and more efficient in returning platelet and RBC to the subject⁴.

One of the main benchmarks of LP quality is the collection efficiency (CE) defined as the ratio between total CD34+ cells yield in apheresis and total CD34+ cells in the processed blood volume (PBV)⁵. The following formula is currently use:

$$CE_{CD34+} = \frac{\text{Collected CD34} + (\text{cells} \times 10^4)}{\left\{ \frac{[\text{preLP CD34} + (\text{cells/mL}) + \text{postLP CD34} + (\text{cells/mL})]}{2} \right\} \times \text{PBV} \}$$

Obtaining the highest possible CE for every LP procedure is critical as long as several studies have shown the importance of targeted CD34+ cells yield in order to assure a safe and rapid haematological recovery after the high dose chemotherapy regimens used in HSCT⁶. Therefore the objective is to reach the target PBSC yield in the safest and quickest way possible: an high CE allows to reduce the PBV and the procedure length.

The CE values are affected by different factors among which blood sample's physical properties. Such factors have been widely studied in MNC protocol⁷, but less studies concern the cMNC protocol⁸. In 147 consecutive apheresis procedures performed both on patients and healthy donors with Spectra Optia (Terumo BCT) with cMNC system, Kondo et colleagues found a moderate positive correlation between CD34+ CE and hematocrit (Ht) and only a very weak correlation with white blood cells (WBC) and platelet counts. We would like to confirm these data in a setting of subjects with a predominance of patients over healthy donors, thus evaluating the influence of clinical and biochemical factors on CE for autologous and allogenic hematopoietic stem cell production. Finally we would like to assess a possible pre-LP Ht threshold associated with a sufficient (> 60%) CD34+ CE⁹.

Dipartimento Area dei Servizi
SC Medicina Trasfusionale

Direttore: [name]

Tel. Segreteria Direzione: [name]

E-mail: [contact]; [contact]

7. Objectives of the study

7.1 Primary objective

In this study we will evaluate the impact of clinical and biochemical factors on Collection Efficiency (CE) for autologous and allogenic hematopoietic stem cell production using the cMNC system.

7.2 Secondary objectives

- Identify clinical and/or biochemical factors associated with an optimal ($\geq 60\%$) CD34+ CE
- Confirm data, from the published literature, regarding the correlation between Ht and CD34+ CE in a cohort of subjects largely composed by hematological patients.
- Develop a prediction model for optimal ($\geq 60\%$) CD34+ CE using pre-LP clinical and/or biochemical factors.

8. Methods

8.1 Study Design

This is an observational, retrospective, non-pharmacological, single-center, no profit study conducted on cohort of patients and stem cell donors referred to the Transfusional Medicine Department of IRCCS Ca' Granda Ospedale Maggiore Policlinico in Milan for PBSC harvesting.

8.1.1 Primary Endpoint

Impact, measured by statistical correlation, of clinical (age, sex, type of donor, diagnosis, recent RBC transfusion) and biochemical (pre-LP values of Ht, Hb, WBC and PLT) variables on CD34+ CE.

8.1.2 Secondary Endpoints

- Correlation of clinical (age, sex, type of donor, diagnosis, recent RBC transfusion) and biochemical variables (pre-LP values of Ht, Hb, WBC and PLT) with an adequate ($\geq 60\%$) CD34+ CE.
- Correlation of pre-LP Ht levels and recent (≤ 60 days) RBC transfusion with CD34+ CE, especially in the autologous setting.
- AUROC (Area Under the ROC Curve) of a pre-LP model based on clinical parameters aimed at predicting an adequate ($\geq 60\%$) CD34+ CE.

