8.2.1 Study Population

We will consider consecutive patients and donors referred to the Apheresis Unit within the Transfusional Medicine Department of Fondazione IRCCS Ca' Granda Ospedale Maggiore Policlinico in Milan (from 1/1/2021 to 31/12/2022) for PBSC collection. Total study population: 113 subjects of which 74 hematological/non hematological patients and 39 stem cell donors.

Patients are defined as subjects affected by a hematological or non-hematological disease for which an autologous stem cells transplantation is recommended. These cases are referred as autologous use of stem cells.

Stem cells donors are volunteer healthy subjects who have decided to undergo the procedures needed to collect blood stem cells. These subjects can donate their blood stem cells in favor of a blood relative or, through subscription of a specific registry (IBMDR – International Bone Marrow Donor Registry), to an unknown subject. These cases are referred as allogenic use of stem cells.

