8.7 Statistical Analysis

For descriptive analyses, quantitative variables will be expressed as mean and standard deviation or as median, interquartile range (IQR) and minimum-maximum range, while categorical variables will be expressed as absolute and relative frequencies.

Aiming to evaluate the impact of clinical and biochemical variables on CD34+ CE, we will examine the association between CD34+ CE and age, sex, type of donor (patients vs healthy donors), hematocrit, hemoglobin level, WBC counts, platelets count.

Analysis will be performed by fitting data in generalized linear models for continuous variables and logistic regression for binary variables. In order to avoid overfitting, the selection of variables to be included in multivariable models will be performed by Backward stepwise regression. All models will be adjusted for significant clinical confounders.

Statistical analysis will be performed using the JMP Pro 16.0 Statistical Analysis Software (SAS Institute, Cary, NC). P values <0.05 (two tailed) were considered statistically significant.

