8.7.2 Secondary Endpoint: Analysis

The association of biological variables with adequate CD34+ CE will be evaluated using linear logistic model of regression and strength of correlation was assessed evaluating Odds Ratio values. Accuracy of clinical prediction model for optimal CD34+ CE will be evaluated by estimating AUROC.

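### The secondary endpoint on haematocrit, recent RBC transfusion and CE in the autologous setting has no matching analysis; the only stated model of continuous CE can drop haematocrit or type of donor and does not list transfusion

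*Combined protocol and SAP*

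**What the plan says.** - **Objective (7.2):** "Confirm data, from the published literature, regarding the correlation between Ht and CD34+ CE in a cohort of subjects largely composed by hematological patients". The background section gives the reason: "We would like to confirm these data in a setting of subjects with a predominance of patients over healthy donors". It describes the cited result as a moderate positive correlation in 147 procedures on patients and healthy donors, and gives no numerical r.
- **Endpoint (8.1.2):** "Correlation of pre-LP Ht levels and recent (≤ 60 days) RBC transfusion with CD34+ CE, especially in the autologous setting".
- **Population (8.2.1, repeated in 8.5):** "Total study population: 113 subjects of which 74 hematological/non hematological patients and 39 stem cell donors".
- **Variables to be examined against CE (8.7):** "age, sex, type of donor (patients vs healthy donors), hematocrit, hemoglobin level, WBC counts, platelets count". Recent RBC transfusion and diagnosis are not in this list, although 8.1.1 names both and 8.3 collects both.
- **Selection (8.7, 8.7.1):** multivariable models are chosen by backward stepwise regression. No term is protected from removal and no removal criterion is stated. Models are to be adjusted for significant clinical confounders, which are not named.
- **Secondary analysis (8.7.2):** "The association of biological variables with adequate CD34+ CE will be evaluated using linear logistic model of regression", plus an AUROC for the prediction model. Section 8.7.4 (supplemental analysis) is marked NA.

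**The concern.** The Ht endpoint concerns CE as a continuous quantity and singles out autologous collections. The analysis sections give it no model, subgroup, interaction or protected term. Whatever the study reports on it must come from the stepwise model built for the primary endpoint. Three things can then go wrong.

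1. Ht can be removed in favour of Hb, which carries almost the same information. No adjusted Ht coefficient would then remain to set beside the published correlation.
2. Type of donor can be removed. If donors have both higher Ht and higher CE, Ht then partly stands in for donor status.
3. Recent RBC transfusion, the other half of the endpoint, may never enter a model of CE.

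At stake is whether the study can say anything specific about Ht and CE in autologous patients, as its endpoint promises.

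**Working it through.** **Figures in the plan.** 74 + 39 = 113. Patients are 74/113 = 65.5% and donors 39/113 = 34.5%. The plan has no power or precision calculation to reproduce, and no means or SDs for Ht or CE. Every input below other than these counts, the seven listed variables and the 0.05 level is an assumption, used only to show size.

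**1. Can selection lose a real Ht effect?** Simulation with n = 113, the seven variables listed in 8.7, assumed removal at p ≥ 0.05, assumed Ht–Hb correlation ρ of 0.90 to 0.98, a true Ht–CE correlation r of 0.3 to 0.5, and the other variables unrelated to CE; 3,000 runs per cell. Entries are the percentage of runs with Ht removed, with the percentage in which Hb was kept instead in brackets.

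| ρ | r = 0.3 | r = 0.4 | r = 0.5 |
|---|---|---|---|
| 0.90 | 30.5 (21.2) | 16.2 (15.5) | 10.3 (10.3) |
| 0.95 | 38.2 (29.8) | 22.7 (22.3) | 17.5 (17.5) |
| 0.98 | 41.5 (32.9) | 34.0 (33.4) | 27.9 (27.9) |

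A repeat gave 9% in the lowest cell, so the range is about 9% to 42%.

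**2. Can donor mix create an Ht effect?** If type of donor is not in the model and the within-group correlation is zero, the pooled correlation is

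r = p(1−p)·d_Ht·d_CE / √{[1 + p(1−p)d_Ht²][1 + p(1−p)d_CE²]},

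with p = 39/113, p(1−p) = 0.226, and shifts d in within-group SDs.

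- d_Ht = 1, d_CE = 0.5: 0.113/√(1.226 × 1.057) = 0.10.
- d_Ht = 1.5, d_CE = 1: 0.339/√(1.509 × 1.226) = 0.25.

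For the stepwise model itself, assume Ht 42 (SD 3.5) in donors and 33 (SD 4) in patients, CE SD 12, donors' CE 5 to 8 points higher, no within-group Ht effect, and Hb excluded. Stepwise selection declares a positive Ht effect in about 9% to 11% of datasets. With Ht and type of donor both forced in, the rate in the same direction is about 2.5% to 3%. A repeat with 6,000 datasets per scenario gave 13% and 10% for stepwise and 2.6% and 2.3% with both forced in. Roughly one in ten is the fair reading. Type of donor was removed in about half of the datasets at a 5-point gap and about 17% at 8 points.

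**3. Is an autologous-only estimate precise enough?** Fisher z: 95% CI = tanh(atanh r ± 1.96/√(n−3)), with 1/√71 = 0.1187 for n = 74 and 1/√110 = 0.0953 for n = 113.

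- r = 0.40, n = 74: tanh(0.4236 ± 0.2326) = 0.19 to 0.58.
- r = 0.40, n = 113: tanh(0.4236 ± 0.1869) = 0.23 to 0.54.
- r = 0.30, n = 74: tanh(0.3095 ± 0.2326) = 0.08 to 0.49; power 74%.
- Smallest r with 80% power at n = 74: tanh[(1.960 + 0.842) × 0.1187] = 0.32 (0.26 at n = 113).

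These intervals are for the simple correlation. The adjusted coefficient will have its own precision.

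**The case against.** Several counter-arguments have weight.

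- **Pooling follows from the design.** A reader might infer that the aim is to show the relation in patients only, so that a pool with 34.5% donors is itself a defect. The documents do not say so. Section 7.2 and the background ask for a cohort in which patients predominate, and 65.5% meets that. The cited study was also mixed, so a pooled estimate is the like-for-like comparison. What remains is the autologous emphasis in 8.1.2, which nothing in 8.7 delivers.
- **An Ht estimate may still be reported.** Section 8.7 says the association of CE with each listed variable will be examined, and ties selection to multivariable models. Single-variable results may be intended, so it cannot be claimed that no Ht estimate will exist. But such an analysis is not stated, and as described it would be pooled and unadjusted for donor type.
- **A larger error rate is tempting.** On the assumptions in step 2, a simple pooled correlation is significant in 32% to 68% of datasets. That does not describe the stated plan, whose only model of continuous CE is the stepwise one. There the excess is modest.
- **Confounder adjustment is promised.** Type of donor is an obvious candidate, but the confounders are unnamed and their inclusion appears to depend on significance.
- **The study is small, retrospective and descriptive (8.5, 8.9).** This stands and bears on severity. Section 8.9 also concedes that the influence of transfusion cannot be clearly assessed. That limits interpretation of the transfusion coefficient, but does not explain why the Ht endpoint has no analysis.

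**Conclusion.** The point holds on the text: a named secondary endpoint has no matching analysis, and the one model that could serve it protects neither Ht nor type of donor and does not list recent RBC transfusion. The consequences in size are a real Ht effect lost in about 9% to 42% of runs, and a false positive Ht effect in roughly one run in ten instead of about 2.5% to 3%. Both depend on assumed values for the Ht–Hb correlation, the removal threshold and the donor–patient differences. They illustrate the risk and do not predict the result. This is a should-fix: it affects one secondary endpoint of a descriptive study and leaves the primary endpoint in place. The documents do not support the stronger readings that pooling contradicts the objective or that the study is bound to produce no Ht estimate.

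**What to change.** Add to section 8.7.2:

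> In the 74 autologous subjects, continuous CE will be modelled on pre-LP Ht and recent (≤ 60 days) RBC transfusion, with age, sex, WBC and platelets as fixed covariates, Hb left out and no variable selection. The Ht and transfusion coefficients, and the Pearson and Spearman correlations for Ht, will be reported with 95% CIs. In the pooled 113 subjects, Ht and type of donor will both be forced in (Hb left out), and an Ht × type-of-donor interaction will be reported as supportive.

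The autologous model has six coefficients besides the intercept, about 12 subjects for each (74/6). All its variables are already collected under 8.3. The cost is one paragraph, two small models and some precision: at r = 0.40 the interval is 0.19 to 0.58 in the 74 patients against 0.23 to 0.54 in all 113, and at r = 0.30 the patient-only interval is 0.08 to 0.49. The pooled model keeps the comparison with the mixed cohort of the cited study.

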8.2 Setting

Dipartimento Area dei Servizi
SC Medicina Trasfusionale

Direttore: [name]

Tel. Segreteria Direzione: [name]

E-mail: [contact]; [contact]

Data will be collected from hospital official documents record (Order Entry, Amb Web, Concerto, Emonet), considering patients referred to the Apheresis Unit (SC Medicina Trasfusionale) for two years' time (from 1/1/2021 to 31/12/2022). All patients are referred to Fondazione IRCCS Ca' Granda Ospedale Maggiore Policlinico in Milan, Italy. Data will be pseudonymized: at enrollment each participant will be assigned a unique code so that only local investigators will be able to identify the subject.

8.2.1 Study Population

We will consider consecutive patients and donors referred to the Apheresis Unit within the Transfusional Medicine Department of Fondazione IRCCS Ca' Granda Ospedale Maggiore Policlinico in Milan (from 1/1/2021 to 31/12/2022) for PBSC collection. Total study population: 113 subjects of which 74 hematological/non hematological patients and 39 stem cell donors.

Patients are defined as subjects affected by a hematological or non-hematological disease for which an autologous stem cells transplantation is recommended. These cases are referred as autologous use of stem cells.

Stem cells donors are volunteer healthy subjects who have decided to undergo the procedures needed to collect blood stem cells. These subjects can donate their blood stem cells in favor of a blood relative or, through subscription of a specific registry (IBMDR – International Bone Marrow Donor Registry), to an unknown subject. These cases are referred as allogenic use of stem cells.

8.2.2. Inclusion Criteria

Subjects must meet all the following inclusion criteria:

Patients and stem cell donors:

- Patients and stem cell donors who have been evaluated as suitable for PBSC apheresis and collection, either for autologous or allogenic use
- Patients and stem cell donors that have completed at least one CD34+ apheresis procedure at Fondazione IRCCS Ca' Granda Ospedale Maggiore Policlinico in Milan.
- Age ≥ 16 years

8.2.3 Exclusion Criteria

- Patients affected by Acute Lymphoblastic Leukemia.

Dipartimento Area dei Servizi
SC Medicina Trasfusionale

Direttore: [name]

Tel. Segreteria Direzione: [name]

E-mail: [contact]; [contact]

8.2.4 Description of study subject

All procedures performed during the study will comply with current clinical practice, international and national guidelines. Main object of the study is the PBSC apheresis procedure performed by using the continuous mononuclear cells collection (cMNC) system with Spectra Optia (Terumo BCT), specifically the biological and clinical factors affecting the procedure efficiency.

8.2.5 Programmed visits and evaluations

Given the retrospective nature of the study, the visits and evaluations already took place between January 2021 and December 2022 during normal clinical activities and as required by practice for the management of patients in this clinical situation.

Patients and stem cell donors were evaluated as suitable for apheresis procedures with out-patient visits at Apheresis Unit within the Transfusional Medicine Department.

Specifically, to exclude any significant comorbidity, all stem cell donors have undergone the following evaluations:

- Record of complete familiar and personal anamnesis, patient's demographical parameters
- Medical examination
- Blood exams including: complete blood count and leukocyte formula, renal and liver function, coagulation tests, serology (HIV, HBV, HCV, syphilis et al), molecular biology (HIV, HBV and HCV), blood group, electrolytes, protein electrophoresis, iron status, vitamin B12, folic acid, lymphocyte subpopulations.
- Chest X-ray
- Full abdomen ultrasound
- Color-doppler echocardiography
- Specialist cardiologic evaluation comprehensive of ECG.
- In case of PBSC donors: specialistic anaesthesiologic evaluation.

Patients, already been extensively evaluated by the reference specialists for all significant comorbidities, have undergone the following evaluations:

- Medical examination and concomitant evaluation of vascular access adequacy.
- Blood exams including: complete blood count and leukocyte formula, renal and liver function, coagulation tests, electrolytes.

8.3 Variables

Dipartimento Area dei Servizi
SC Medicina Trasfusionale

Direttore: [name]

Tel. Segreteria Direzione: [name]

E-mail: [contact]; [contact]

The following variables will be collected:

- Clinical parameters: age (years), gender (male or female), body weight (kg), type of PBSC use (autologous or allogenic), date of apheresis procedure, type of venous access (peripheral veins or central venous access), total hematic volume (liters), type of mobilization (chemotherapy, G-CSF, Plerixafor), diagnosis (only for autologous setting: multiple myeloma, non-hodgking lymphoma, non haematological disease), RBC transfusion within 60 days before apheresis (yes or not).
- Biochemical parameters: complete blood count pre-LP (cell/mcL), complete blood count on apheresis product (cell/mcL), CD34+ count pre-LP, post-LP and in apheresis product (cell/mcL; cellx106 and cellx106/kg).
- Procedures parameters: total blood volume processed (L), total apheresis product volume (mL)

8.4 Documents source

All data will be collected from official hospital records, particularly AmbWeb, and stored in an ad hoc file. Patient's identity will be managed through an alphanumeric code.

8.5 Sample Size

Total study population: 113 subjects of which 74 hematological/non hematological patients and 39 stem cell donors.

The number of subjects evaluated is determined by the clinical activity of the Apheresis Unit (SC Medicina Trasfusionale) and has been considered adequate considering the number of subjects included in other similar study present in the literature^{7,8}. Due to descriptive nature of the analysis planned, no pre-analysis sample size was determined.

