8.9 Study Limits

We will try to correct two possible bias within our cohorts:

- by excluding patients affected by Acute Lymphoblastic Leukemia who underwent apheresis procedure in order to collect a salvage CD34+ autologous backup. Those patients are characterized by abnormally high pre-LP CD34+ counts due to disease immunophenotype (often CD34+) and low bone marrow disease burden. Moreover the practice of collecting an autologous CD34+ backup in case of allogeneic engraftment failure or disease relapse, although not detrimental for patients, it's not supported by strong practicing evidence.
- By considering only the first apheresis procedure for each patients in order to avoid any possible selective bias.

The main limits of this study could be:

- the small cohort dimension which do not allow significant evaluations about influence of underlying disease, mobilization regimens and poor mobilizing condition.
- the retrospective nature of data which do not allow to clearly assess influence and utility of RBC transfusion pre-LP.

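### Section 8.5 calls 113 subjects adequate and the analysis descriptive, but the plan is inferential; 113 suits the primary linear analysis, not a 7 to 10 parameter prediction model or the effect of diagnosis

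*Combined protocol and SAP*

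**What the plan says.** - **Section 8.5** gives the size: "Total study population: 113 subjects of which 74 hematological/non hematological patients and 39 stem cell donors". It says this was set by the unit's clinical activity and "has been considered adequate considering the number of subjects included in other similar study present in the literature". It adds: "Due to descriptive nature of the analysis planned, no pre-analysis sample size was determined".
- **Section 7.2** sets an objective to "Develop a prediction model for optimal" CE, meaning CE of at least 60%. Section 8.1.2 makes the AUROC of that model an endpoint.
- **Section 8.7** plans generalized linear and logistic models, with variables chosen by backward stepwise regression, and states: "P values <0.05 (two tailed) were considered statistically significant". Sections 8.7.1 and 8.7.2 add estimates with standard errors, odds ratios and the AUROC.
- **Section 8.1.1** lists nine primary-endpoint factors, diagnosis among them. The list in 8.7 has seven and leaves out diagnosis and recent RBC transfusion.
- **Section 8.9** keeps only the first procedure per patient and names as a limit "the small cohort dimension which do not allow significant evaluations about influence of underlying disease, mobilization regimens and poor mobilizing condition".

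**The concern.** Three statements do not fit together.

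1. The reason given in 8.5 for making no size assessment is that the analysis is descriptive. Section 8.7 itself treats descriptive summaries separately from the regression models and tests that carry the endpoints.
2. The adequacy statement in 8.5 covers every analysis. Section 8.9 withdraws it for underlying disease, which 8.1.1 includes in the primary endpoint.
3. Nothing in 8.5 separates the linear analysis of continuous CE from the binary prediction model, although they make very different demands on 113 observations.

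A reader who relies on 8.5 could take a null result for diagnosis as evidence of no effect. The same reader could take the AUROC of the fitted model as a fair estimate of how it would perform in new subjects.

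**Working it through.** The plan gives no power, effect size or event share, so there is no calculation to reproduce. The only check on its own figures is 74 + 39 = 113, which agrees.

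**Inputs from the documents.** N = 113, of whom 74 are patients (8.5); one procedure per subject (8.9); two-sided alpha 0.05 (8.7). There are 7 parameters from the list in 8.7. The list in 8.1.1 gives 10: age, sex, type of donor, recent RBC transfusion, Ht, Hb, WBC and PLT at one each, and diagnosis at two, for the three diagnosis groups in 8.3.

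**Assumed inputs.** Correlations of 0.20 to 0.40; half the subjects reaching CE of 60%; true AUROC of 0.70 to 0.80. The shrinkage target of 0.90 is a conventional benchmark.

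**1. Primary linear analysis (Fisher z, SE = 1/√(N − 3)).**

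- SE = 1/√110 = 0.0953 for 113, and 1/√71 = 0.1187 for 74.
- Detectable r at 80% power = tanh[(1.96 + 0.84) × SE] = 0.26 for 113 and 0.32 for 74.
- Power = Φ(atanh(r)/SE − 1.96). With 113 and r = 0.30: Φ(0.3095/0.0953 − 1.96) = Φ(1.29) = 90%. With r = 0.20: Φ(0.2027/0.0953 − 1.96) = Φ(0.17) = 57%. With 74, the powers are 74% and 40%.
- 95% CI at r = 0.40: tanh(0.4236 ± 1.96 × SE) = 0.23 to 0.54 for 113 and 0.19 to 0.58 for 74.
- Adjusting for nine covariates changes little: with 113, the detectable r is 0.27 and power at r = 0.30 is 88%.
- Patients against donors: detectable difference = 2.80 × √(1/74 + 1/39) = 0.55 SD.

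**2. Diagnosis.** It varies only among the 74 patients, and the split is not given. With an assumed split of 40, 25 and 9, the detectable pairwise difference is 2.80 × √(1/40 + 1/25) = 0.71 SD between the larger groups. Against the smallest it is 2.80 × √(1/40 + 1/9) = 1.03 SD. This agrees with the limit conceded in 8.9.

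**3. Prediction model for CE of at least 60%.** The criterion is n = p / [(S − 1) × ln(1 − R²/S)] with S = 0.90. R² is the Cox-Snell value implied by the AUROC when the linear predictor is normal with equal variance in both outcome groups.

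| True AUROC | R² | −0.1 × ln(1 − R²/0.9) | n, 7 parameters | n, 10 parameters | Parameters that 113 supports |
|---|---|---|---|---|---|
| 0.70 | 0.121 | 0.0144 | about 485 | about 690 | 1.6 |
| 0.75 | 0.186 | 0.0232 | about 300 | about 430 | 2.6 |
| 0.80 | 0.262 | 0.0344 | about 205 | about 290 | 3.9 |

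The last column is 113 times the third. If the share is 30% or 70%, 10 parameters need about 820, 510 and 340. By events per parameter, a half share gives 56.5/7 = 8.1 or 56.5/10 = 5.7, and a 20% or 80% share gives 22.6/7 = 3.2 or 22.6/10 = 2.3.

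**4. Simulation of the modelling strategy.** It used 113 subjects, 10 candidate parameters and half reaching 60%. It also assumed a Ht-Hb correlation of 0.95 and 30% of patients transfused. With only Ht predictive (true AUROC about 0.70), the full model showed about 0.76 in its own data and 0.65 in new data. The backward-selected model showed about 0.72 and 0.68. With no true effects, backward selection still kept at least one factor in about 36% to 40% of datasets, with a mean apparent AUROC of about 0.63.

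**The case against.** **A fixed retrospective cohort needs no prior sample-size calculation.** This stands, and 8.5 is open that clinical activity set the number. What is missing is a statement of what that number can deliver.

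**The primary analysis is reasonably served.** This also stands. CE is continuous, and 113 subjects give 11 (113/10) to 16 (113/7) subjects per parameter. A detectable correlation of about 0.26 applies to age, Hb, WBC and PLT as much as to Ht. A reader might infer that the cohort cannot support multivariable models at all, or supports nothing beyond the Ht correlation. The figures do not bear that out.

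**Section 8.9 already warns about underlying disease.** It does, and this softens the risk of misreading. It does not remove the conflict with 8.1.1 or with the unqualified statement in 8.5.

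**Ten parameters is the largest case.** Section 8.1.2 describes the prediction model as based on clinical parameters, whereas 7.2 allows clinical and/or biochemical ones. Six clinical parameters would need 6/0.0144, 6/0.0232 and 6/0.0344, or about 416, 259 and 174 subjects. All still exceed 113. Backward selection does reduce the average optimism, as the simulation shows, but does not remove it.

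**The comparison with the literature.** A reader might set 113 against the background's description of a cited study, "In 147 consecutive apheresis procedures performed both on patients and healthy donors", and infer a shortfall. The documents do not support this. They do not say how many subjects lie behind the 147 procedures, and they give no size for the other study on which 8.5 relies. The adequacy claim is unquantified, but it is not shown to be false by comparison.

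**Conclusion.** The concern holds in a limited form. Two parts rest on the text alone: the descriptive rationale in 8.5 conflicts with the analyses in 8.7 to 8.7.2, and the blanket adequacy statement conflicts with 8.9 on a factor that 8.1.1 puts in the primary endpoint. The third part rests on the assumed share reaching 60%, the assumed AUROC and the conventional shrinkage target. At AUROC 0.70 to 0.80 with half the subjects reaching 60%, a model with 7 to 10 candidates needs roughly 1.8 (205/113) to 6.1 (690/113) times the available subjects. Uneven shares make this worse. The size of the primary linear analysis is not in question for correlations of about 0.26 or more. For weaker ones, such as 0.20, power is only 57% with 113 subjects and 40% with 74.

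**What to change.** - **Section 8.5:** delete the descriptive rationale and the unqualified adequacy claim. State instead the precision for the primary correlations: with 113 subjects, 80% power for r of about 0.26 and a 95% CI of 0.23 to 0.54 at r = 0.40; with 74, about 0.32 and 0.19 to 0.58.
- **Sections 8.1.1, 8.7 and 8.9:** give diagnosis one status throughout. Make it exploratory, reported as mean CE with 95% CI by diagnosis.
- **Sections 8.7 and 8.7.2:** limit the prediction model to at most two or three parameters named before CE is examined, for example Ht and type of PBSC use, in place of backward selection from all factors. Report a bootstrap optimism-corrected AUROC and label the model exploratory.

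The cap alone is not enough. At a half share, three parameters meet the 0.90 criterion with 113 subjects only from an AUROC of about 0.77. Two meet it at 0.75 (2/0.0232, about 86 subjects) but not at 0.70 (2/0.0144, about 139). Hence the optimism correction and the label.

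The cost is changed wording and a short bootstrap analysis, with no added subjects. The price is a less favourable adequacy statement and fewer factors in the prediction model.
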